7.2.2 Discontinuation of Study Treatment and End of Treatment Visit

Patients may voluntarily discontinue from the study treatment for any reason at any time. If a patient decides to discontinue from the study treatment, the investigator should make every effort to determine the primary reason for this decision and record this information in the patient's chart and on the appropriate eCRF pages. Other reasons for discontinuation of study treatment are outlined in [Section 6.10](#).

Patients will be considered withdrawn from therapy if they state an intention to withdraw, and fail to return for visits or become lost to follow-up for any other reason.

The investigator should discontinue study treatment for a given patient if, on balance, he/she believes that continuation would be detrimental to the patient's well-being.

At the time patients discontinue study treatment, a visit should be scheduled as soon as possible, and within 14 days of the last dose of study drug or within 14 days of the decision to permanently discontinue study treatment, at which time all of the assessments listed for the EOT visit will be performed ([Table 7-1](#)). If the decision to withdraw the patient occurs at a regularly scheduled visit, that visit may become the EOT visit rather than having the patient return for an additional visit. An End of Treatment Phase Disposition eCRF page should be completed, giving the date and reason for stopping the study treatment. End of treatment/premature withdrawal visit is not considered as the end of the study.

Patients who discontinue study treatment should NOT be considered withdrawn from the study. They should return for the assessments indicated in [Section 7](#) and [Table 7-1](#). If they fail to return for these assessments for unknown reasons, every effort (e.g., telephone, email, postal letter) should be made to contact them. If a patient discontinues study treatment, but continues study assessments, the patient remains on study until such time as he/she completes protocol criteria for ending study

assessments. At that time, the reason for study completion should be recorded on the Study Disposition eCRF page.

7.2.3 90-day Safety Follow-up Period

All patients must have safety evaluations 90 days after the last dose of study treatment. Information related to all AEs (including concomitant medication taken for on-going AEs) will be collected for 90 days after the last dose of study drug. All AEs suspected to be related to study treatment should be followed up weekly or as clinically indicated until resolution or stabilization.

Anti-neoplastic therapies since discontinuation of study drug will be collected during this follow-up period.

7.2.4 Disease Progression Follow-up Period

Patients who discontinue study treatment for any reason other than death, disease progression per RECIST v.1.1, lost to follow-up, withdrawal of consent, or study termination, should return for tumor evaluation assessments every 8 weeks until 40 weeks, and then every 12 weeks until progression of disease per RECIST v.1.1.

- All patients who discontinue treatment for reasons other than PD per RECISTv1.1 will be followed with imaging until evidence of PD per RECISTv1.1.
- For patients who consent to and continue treatment beyond progression per RECISTv1.1, imaging should continue until progression per modified irRECIST (irPD) or treatment discontinuation.
- If patients choose not to return for these visits or are unable to do so, every effort should be made to contact them or a knowledgeable informant by telephone to determine if the patient has had disease progression.
- Patients who discontinue treatment for reasons of disease progression by either RECISTv1.1 or modified irRECIST criteria will not enter the Disease Progression Follow-up Period.
- Anti-neoplastic therapies since discontinuation of study drug will be collected during this follow-up period.

See [Table 7-2](#) for additional details on Disease Assessment Collection Plan.

7.2.5 Survival Follow-up Period

Upon completion of the 90-day safety follow up or disease progression follow up, patients will be followed for survival every 12 weeks (can be done by telephone call) until death or until the end of the study is reached, unless they withdraw consent or are lost to follow-up.

Anti-neoplastic therapies since discontinuation of study drug will be collected during the Survival Follow-up period.

For the Phase 2 expansion cohorts, survival calls will be made in the 2 weeks following the date of the data cut-off for any OS reporting. Thus, patients may be contacted more frequently than every 12 weeks at this time. If patients are confirmed to be alive, or if the death date is post the data cut-off date, these patients will be censored at the date of the data cut off in the OS reporting. Death dates may be found by checking publicly available death registries in line with local laws and regulations.

7.2.6 Lost to Follow Up

For patients whose status is unclear because they fail to appear for study visits without stating an intention to withdraw consent, the investigator should show "due diligence" by contacting the patient, family, or family physician as agreed in the informed consent and by documenting in the source documents steps taken to contact the patient, e.g., dates of telephone calls, registered letters, etc, a patient should not be considered lost to follow up until due diligence has been completed. Patients lost to follow up should be recorded as such on the appropriate Patient Disposition eCRF.

7.3 Details of All Assessment Types

7.3.1 Efficacy Assessments

Radiologic assessments should be performed as scheduled every 8 or 12 weeks as indicated in this section (See [Table 7-2](#) below), using a reference to C1D1 and should NOT follow delays incurred in the treatment period.

Tumor response will be determined according to 2 sets of criteria:

1. RECIST v.1.1 ([Appendix 1](#))
2. Modified irRECIST for patients who continue treatment beyond RECISTv.1.1 disease progression ([Appendix 2](#))

For the Phase 1 cohort, the local investigator's assessment will be used for the analysis of response according to RECIST v.1.1 and modified irRECIST for efficacy endpoints of the study, and for treatment decision making (study discontinuation due to PD as per RECISTv.1.1/modified irRECIST).

Independent Central Review: An ICR will be used for the analysis of ORR and all other tumor related endpoints based on RECIST v.1.1 and modified irRECIST for the Phase 2 cohorts. ICR of the Phase 1 cohort may be done on an exploratory basis for patients who have consented to central reading.

PFS will be assessed using RECIST v.1.1. Patients experiencing PD per RECIST v.1.1 criteria may consent to continue to be treated according to irRECIST guidelines until confirmed, unequivocal progression (irPD) is documented via modified irRECIST. Progression based on modified irRECIST will be assessed as an exploratory endpoint.

Investigator assessment data will be used for treatment decision making during the study.

Assessments schedule: At Screening, all patients will undergo CT or MRI with IV contrast of the chest, abdomen, and pelvis. CT imaging is preferred and MRI should only be used to evaluate sites of disease that are not adequately imaged by CT. If a patient is intolerant of iodine-based contrast agents, CT may be performed without contrast. Visible skin lesions and easily palpable subcutaneous tumors may be measured by physical examination using a ruler or calipers. Ultrasound should not be used to

measure sites of disease. For a given target lesion, the same imaging modality should be used throughout the study (CT or MRI). See Table 7-2 for further details.

Tumor assessments will be performed at the following time points:

- Screening
- Every 8 weeks \pm 1 week from C1D1 to 40 weeks (C11D1), then every 12 weeks (3 cycles) until PD per RECIST v.1.1 or discontinuation of study treatment. Note: For patients who continue treatment beyond progression per RECISTv.1.1, imaging should continue until disease progression per modified irRECIST.
- Partial response, minor response (MinR), or complete response (CR), per both RECIST v.1.1 and modified irRECIST, should be confirmed by a new assessment after at least 4 weeks. For patients who continue treatment beyond progression by RECISTv1.1, PD per modified irRECIST (irPD) should be confirmed after at least 4 weeks from PD by RECISTv.1.1. Further confirmation of irPD after its initial occurrence is not required but may be done at Investigator discretion.
- At EOT, if a scan was not conducted within 30 days prior to EOT. Note, if a patient discontinues treatment, but remains in Disease Progression Follow Up, then imaging visits should continue as per the original study plan and schedule and will not be needed at the EOT visit.

Disease progression follow-up should be performed as described in [Section 7.2.4](#).

Table 7-2 Disease Assessment Collection Plan

Procedure	Screening/Baseline	During Treatment/Follow Up
CT or MRI with contrast enhancement (chest, abdomen, pelvis)	Mandatory	Mandatory, every 8 weeks from C1D1 until C11D1 (40 weeks), then every 12 weeks until progressive disease per RECISTv1.1, irPD per modified irRECIST for patients who continue treatment beyond PD per RECISTv1.1 or discontinuation of study treatment The same imaging modality should be used throughout the study (CT or MRI) At EOT, if a scan was not conducted within 30 days prior to EOT. Note, if a patient discontinues treatment, but remains in Disease Progression Follow Up, then imaging visits should continue as per the original study plan/schedule and will not be needed at the EOT visit
Brain MRI with contrast	Required only if clinical suspicion of brain metastasis at Screening	If disease was detected at Baseline, or if clinically indicated

C#D# = Cycle # Day #; CT = computed tomography scan; EOT = end of treatment; MRI = magnetic resonance imaging; RECISTv1.1 = Response Evaluation Criteria in Solid Tumors version 1.1.

7.3.1.1 Independent Central Review

All on-study images acquired for tumor and treatment effect assessments will be submitted to an imaging contract research organization (CRO) for further blinded, independent, central review for analysis. A central imaging manual will be provided to all investigative sites detailing the procedures for de-identification and submission of imaging studies for central review. For endpoints assessed by ICR, review of all radiological imaging data will be carried out. All radiological scans for all patients (including those at unscheduled visits, or outside visit windows), will be provided to the ICR. Further details of the ICR procedures and processes will be included in the study imaging manuals.

All patient management decisions will be based upon local assessment of imaging studies at the site and not on the ICR.

7.3.2 Safety and Tolerability Assessments

Safety will be monitored by assessing physical examination, vital signs, body height and weight, performance status, hematology, chemistry, coagulation, urinalysis, thyroid function, pregnancy, ECG, cytokine testing. AE are collected at every visit. For details on AE collection and reporting, refer to [Section 8](#).

7.3.3 Physical Examination

Physical examination will be performed according to [Table 7-1](#).

At Screening and C1D1, prior to IMCgp100 infusion, a complete physical examination will be performed and will include the examination of general appearance, skin, neck (including thyroid), eyes, ears, nose, throat, lungs, heart, abdomen, back, lymph nodes, extremities and neurological system. If indicated based on medical history and/or symptoms, rectal, external genitalia, breast, and pelvic exams will be performed.

From C1D8 onwards, a short physical examination will be performed prior to IMCgp100 infusion. A short physical exam will include the examination of general appearance, vital signs (temperature, blood pressure, respiratory rate and pulse) and body sites as directed by symptoms.

Significant findings that were present prior to the signature of the informed consent must be included in the Medical History eCRF page. Significant new findings that begin or worsen after informed consent must be recorded on the AE eCRF page.

7.3.4 Vital Signs

Vital signs (body temperature, pulse rate, respiratory rate, and blood pressure) must be performed before dosing and after the IMCgp100 administration as indicated in [Table 7-1](#) and [Table 7-3](#), and as per institutional standards.

Vital signs should be assessed on the scheduled day, even if study treatment is being withheld. More frequent examinations may be performed at the discretion of the investigator if medically indicated, and will be recorded as unscheduled assessments.

See [Section 6.2](#) for additional details on intra-patient dose escalation regimen.

Table 7-3 Post Dose Vital Signs Monitoring

C1D1, C1D8, C1D15 Inpatient monitoring required for all patients	Vital signs monitored per institutional standards at a minimum of every 4 hours . Patients should be monitored for at least 16 hours after dosing. 
 • Patients experiencing Grade 2 or greater hypotension at C1D15 require inpatient monitoring for the subsequent/next C1D22 dose. • Those experiencing Grade 3 or 4 hypotension at C1D1, C1D8 or C1D15 require hourly VS monitoring for minimum of 8 hours after dosing for any doses administered as outpatient through C2D15.
C1D22 Inpatient monitoring required for exception noted	Patients experiencing a grade 2 or greater hypotension at C1D15 must be observed as an inpatient for C1D22 dose, with VS performed at a minimum of every 4 hours and monitoring for at least 16 hours after dosing.
C1D22 through C2D15 Monitoring requirements for exceptions noted	Patients experiencing Grade 3 or 4 hypotension at C1D1, C1D8 or C1D15 require hourly VS monitoring for minimum of 8 hours after dosing for any doses administered as outpatient through C2D15. 
 • If patient experienced ≥ Grade 2 hypotension at C1D15, they must be monitored as inpatient for C1D22, as noted above.
C2 and later cycles- Days 1, 8, 15 and 22 Outpatient monitoring	For patients without Grade 2 or greater hypotension at C1D15 or Grade 3 or 4 hypotension at C1D1, C1D8 or C1D15 , outpatient VS must be monitored in clinic for minimum of one hour after infusion with at least 2 post-dose VS measurements performed. 
For patients who have received outpatient treatment with IMCgp100 for at least 3 months, outpatient monitoring in clinic may be decreased to minimum of 30 minutes post dosing after discussion with Sponsor Medical Monitor.

Treatment breaks/delays	Patients with break or delay in treatment for >2 weeks AND with history of a grade 3 or 4 hypotension with IMCgp100 dosing during the first weeks of treatment will be monitored as an inpatient for the dose subsequent to/following the break in dosing, with VS performed at a minimum of every 4 hours and monitoring for at least 16 hours after dosing .

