6.2 Summary of Intra-patient Dose Escalation Treatment Regimen

Patients enrolled in this study will receive treatment with single-agent IMCgp100 on C1D1 and C1D8 at 20 mcg and 30 mcg per week, respectively. The majority of moderate-to-severe toxicity associated with IMCgp100 in the FIH study was observed at these 2 dose time points and included hypotension, rash, pruritus, fever, and chills (please refer to [Section 1.4](#), Clinical Experience with IMCgp100 for a full discussion of the safety data with IMCgp100). After this initial dosing period, beginning at C1D15, patients will receive an escalated dose of IMCgp100 according to the cohort into which they are enrolled (please see [Table 6-2](#) below, for dose levels to be tested). This escalated dose administered at C1D15 will be the dose used for the remainder of the treatment period unless dose reduction is implemented for toxicity. See schematic for intra-patient dose escalation regimen described in [Section 3.1](#) and [Figure 3-1](#).

In this intra-patient escalation regimen, all patients will require overnight inpatient hospitalization and a minimum of pre-dose and monitoring vital signs every 4-hours after the first administration of IMCgp100 (C1D1), after the second administration (C1D8), and after the escalated dose of IMCgp100 on C1D15 is administered. For the first 3 administrations of IMCgp100, patients should be monitored for at least 16 hours after dosing. “Inpatient hospitalization” refers to a facility with fully functional resuscitation facilities, 24 hour monitoring and physician availability.

Inpatient monitoring at Cycle 1 Day 22 (C1D22) will be determined by the toxicity observed in the C1D1–C1D15 doses as follows:

1. If the escalated dose at C1D15 administered as an inpatient does not raise safety concerns (and the patient does not experience an adverse reaction involving hypotension of grade 2 or greater), the subsequent dose at C1D22 and all subsequent doses can be administered on an outpatient basis
2. If the patient experiences hypotension requiring any medical intervention (Common Terminology Criteria for Adverse Event [CTCAE] grade 2 or greater) at C1D15, then the C1D22 dose must be administered with inpatient monitoring, similar to C1D1–C1D15. If the patient does not experience hypotension requiring medical intervention at the C1D22 dose administered as an inpatient, then all subsequent doses can be administered on an outpatient basis

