3. Hospitalization at other days (e.g., Cycle 2 and beyond) are determined at the discretion of the principal investigator based on the patient's history and tolerance for the initial doses of the study medication with the exception of patients experiencing a treatment delay (please refer to bullet 5 below)
4. Until Cycle 2 Day 15 (C2D15), patients who have experienced a prior CTCAE grade 3 or 4 hypotension event with IMCgp100 dosing and are receiving a dose in the outpatient setting, must be observed in the clinic for a minimum of 8 hours after completion of the IMCgp100 dose.
5. Patients experiencing a break or delay in treatment for any reason of more than 2 weeks AND have a history of a grade 3 or 4 hypotension event with IMCgp100 dosing during the first weeks of treatment will be monitored as an inpatient for the dose subsequent to the break in dosing, regardless of the timing of the break in dosing.

Due to the risk of hypotension, all patients receiving anti-hypertensive medications must **discontinue all anti-hypertensive therapy** for 24 hours prior to dosing and for 24 hours after dosing for the first 6 QW doses of IMCgp100 unless discussed and agreed with the Sponsor's Medical Monitor. After the sixth weekly dose, anti-hypertensive therapy can be restarted on a continuous basis thereafter with the dosing of IMCgp100 (eliminating the 24 hour hold during IMCgp100 dosing) at the discretion of the principal investigator.

In addition, due to the risk of hypotension, IV fluids may be administered prior to IMCgp100 administration and, if given, IV fluids will be recorded as a concomitant medication in the eCRF. The administration of IV fluids should be guided by clinical evaluation and the volume status of the patient. Pruritus is a common adverse event with IMCgp100, so premedication with an antihistamine may be considered. See [Table 6-3](#) for further recommendations regarding treatment of skin toxicity. If a patient experiences an infusion reaction, he/she may receive premedication on subsequent dosing days after consultation with the Sponsor Medical Monitor. Pre-medications should include, but are not limited to, paracetamol/acetaminophen and an antihistamine. Corticosteroid premedication should be avoided; corticosteroids should only be considered if the paracetamol/acetaminophen and antihistamine combination is not effective and only after consultation with the Sponsor Medical Monitor.

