Moderate, asymptomatic decrease ² : e.g., ≥ 15 mmHg, but < 35 mmHg systolic blood pressure Grade 2	
Increase frequency of vitals to every 1 to 2 hours, or more frequently as medically necessary.
 
Monitor fluid balance status with careful attention to clinical volume status, as assessed by degree of peripheral edema or rales on pulmonary examination.
 
Administer bolus intravenous fluids at a rate of approximately 1 L crystalloid per hour. If the patient is asymptomatic and non-orthostatic after infusion of 2–3 L administered over 2–3 hours, consider transition to maintenance intravenous fluids until resolved.
 
If hypotension is not rapidly resolved with intravenous crystalloid therapy, add intravenous corticosteroid therapy of methylprednisolone 2 mg/kg initial dose or equivalent
 
Consider prophylactic electrolyte supplementation for patients receiving intravenous fluids with low-normal serum electrolyte levels.

Moderate, symptomatic decrease ² : e.g., ≥ 15 mmHg and orthostasis Grade 3	
Increase frequency of vitals to every 1 hour, or more frequently as medically necessary.
 
Administer bolus intravenous fluids at a rate of approximately 1 L crystalloid per hour. If the patient has symptomatic orthostatic hypotension after infusion of 2–3 L administered over 2–3 hours, consider administration of corticosteroids such as intravenous methylprednisolone 2 mg/kg or equivalent.
 
Initiate vasopressor therapy as required to maintain blood pressure.

	
Consider prophylactic electrolyte supplementation for patients receiving intravenous fluids with low-normal serum electrolyte levels.
 
If appropriate, consider additional measures according to the institutional cytokine release protocol (also see management of Infusion-related Reactions below).
 
If resolved within 48 hours of onset, no change in dosing is necessary. If repeat hypotension occurs, consult with the Sponsor Medical Monitor prior to subsequent dosing. Please refer to guidance for continued inpatient monitoring to determine need for continued inpatient monitoring (Section 6.2).
 
Consider the diagnosis of cytokine release syndrome and management (below).

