
Severe, symptomatic decrease²: e.g., ≥ 35 mmHg systolic and symptomatic when supine or mean arterial pressure³ ≤ 55 mmHg
 
Grade 4
	
Immediately administer high-dose intravenous corticosteroid therapy of methylprednisolone 2 mg/kg initial dose or equivalent. Maximize vasopressor therapy and fluid management. Administer bolus intravenous fluids (1 L crystalloid as rapidly as feasible) and consider escalation to higher level of care i.e., intensive care unit).
 
Consider maximal immunosuppression with high-dose intravenous corticosteroid therapy and consider additional measures (e.g., anti-IL6, tocilizumab) as required.
 
If appropriate, aggressive fluid therapy as indicated and described above; consider additional measures according to prophylactic electrolyte supplementation for patients receiving intravenous fluids with low-normal serum electrolyte levels.
 
Monitor vital signs every hour until resolved.
 
Consider additional measures according to the institutional cytokine release protocol (also see management of Infusion-related Reactions / Cytokine Release Syndrome below).
 
IMCgp100 must be dose reduced or discontinued. The Sponsor Medical Monitor should be consulted for discussion of individual case management.

Infusion-related Reactions/Anaphylaxis (occurring during infusion)	

Grade 1
	
Administer medications for symptomatic relief as needed. Infusion interruption may be considered until resolution of the event (up to 4 hours). The infusion rate of the study medication may be decreased by 50%. If resolved with decreased rate of infusion, any subsequent infusions can be administered at the reduced rate.

Grade 2
	
Stop infusion and keep intravenous line open. Treat according to institutional practice. Provide all supportive measures as indicated. Provide supplemental oxygen and fluids, as needed.
 
Monitor vital signs (e.g., blood pressure, pulse, and temperature) until resolution. Administer medications for symptomatic relief as needed. Antihistamines, acetaminophen (paracetamol), or corticosteroids may be administered, as needed at the discretion of the investigator.

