PK sampling ^r	7.3.8 Table 7-7		PK sampling to be scheduled according to Table 7-7																		
Immunogenicity sampling ^r	7.3.8 Table 7-7		See Table 7-7 for immunogenicity sampling timing																		
HLA-A2 determination ^s	7.1.1.3	X																			
Survival contact for follow-up	7.2.5																				X

C#D# = Cycle # Day #; DNA = deoxyribonucleic acid; ECG = electrocardiogram; ECOG = Eastern Cooperative Oncology Group; EOT = end of treatment; HLA-A2 = human leukocyte antigen-A2; IFN- γ = interferon gamma; IL-6 = interleukin-6; irRECIST = immune-related response criteria; PD = progressive disease; PK = pharmacokinetic; RECIST = Response Evaluation Criteria in Solid Tumors.

FOOTNOTES:

- a Cycles 4 and greater will follow the same schedule of assessments as outlined for Cycle 3 with exception of tumor imaging which will follow the noted schedule and PK and pharmacodynamic assessments which will follow the schedules in [Table 7-7](#) and [Table 7-8](#), respectively.
- b Patients might be contacted earlier than the 3 month time point for survival follow-up during the interim and final analysis
- c Physical Examination should be done prior to administration of IMCgp100 and from C1D8 onwards, a short physical examination will be performed
- d Overnight inpatient hospitalization and frequent vital signs (minimum of pre-dose and Q4 hours vital signs) are required at C1D1, C1D8, and C1D15. Inpatient monitoring at C1D22 will be determined based on the toxicity profile in the individual patient at C1D15. Patients experiencing a grade 2 or greater hypotension event at C1D15 must be observed as an inpatient for the subsequent C1D22 dose. Patients experiencing a grade 3 or 4 hypotension event during the inpatient monitoring at C1D1, C1D8, or C1D15 will require additional monitoring for any doses administered as an outpatient through C2D15. If patients have experienced grade 3 or 4 hypotension at any of these doses, then outpatient monitoring through C2D15 must be for a minimum of 8 hours after the IMCgp100 dose with vital signs monitored every hour. Please refer to [Section 6.2](#) weekly and [Section 7.3.4](#) for details of overnight hospitalizations and vital signs monitoring.
- e ECOG Performance Status will be determined on Day 1 of every odd-numbered cycle and at EOT.

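### Table 7-3 leaves patients with early hypotension without a stated outpatient observation minimum after C1D22 or C2D15, and its 8-hour trigger is narrower than Section 6.2 item 4

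*Protocol*

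**What the plan says.** Three places in the protocol govern observation after dosing.

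**Section 6.2.** Item 1 covers patients whose inpatient C1D15 dose raised no safety concern and caused no Grade 2 or greater hypotension: "the subsequent dose at C1D22 and all subsequent doses can be administered on an outpatient basis". Item 2 keeps patients with Grade 2 or greater hypotension at C1D15 as inpatients for C1D22. If they have no hypotension requiring medical intervention "at the C1D22 dose administered as an inpatient, then all subsequent doses can be administered on an outpatient basis". Neither item gives an outpatient observation time. Item 3 adds: "Hospitalization at other days (e.g., Cycle 2 and beyond) are determined at the discretion of the principal investigator", guided by the patient's history and tolerance. Item 4 sets eight hours in clinic for outpatient doses: "Until Cycle 2 Day 15 (C2D15), patients who have experienced a prior CTCAE grade 3 or 4 hypotension event with IMCgp100 dosing". Item 5 requires inpatient monitoring of the next dose after a break of more than 2 weeks in patients with a Grade 3/4 history from the first weeks.

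**Section 7.3.4, Table 7-3.** Hourly vital signs for at least 8 hours apply to outpatient doses through C2D15 after Grade 3/4 hypotension at C1D1, C1D8 or C1D15. The row for Cycle 2 and later sets one hour and at least two post-dose measurements for patients "without Grade 2 or greater hypotension at C1D15 or Grade 3 or 4 hypotension at C1D1, C1D8 or C1D15". After at least 3 months of outpatient treatment, clinic monitoring may be cut to 30 minutes following discussion with the Medical Monitor.

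**Table 7-1, footnote d.** It carries the same visit-limited 8-hour trigger as Table 7-3: "If patients have experienced grade 3 or 4 hypotension at any of these doses, then outpatient monitoring through C2D15 must be for a minimum", which it sets at 8 hours.

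**The concern.** Hypotension is a named risk of this drug, and Section 6.2 withholds anti-hypertensives around the first six weekly doses because of it. From Cycle 2, Table 7-3 writes down a minimum for patients without the listed early hypotension and omits one for patients who had it. One would expect the floor to be at least as firm for the second group.

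The trigger mismatch is a separate matter. Amendment 7 added Table 7-3 to clarify vital-sign frequency, so sites may well work from it. A patient whose first Grade 3/4 event comes at C1D22 meets the trigger in Section 6.2 item 4 but not the one in Table 7-3 or footnote d. At stake is the observation of a few patients after a serious event. The sample size, the objective response rate and the other analyses are untouched.

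**Working it through.** The protocol gives no figure to reproduce. The check traces each patient group through the three texts, assuming weekly doses in 28-day cycles, no delays, and outpatient dosing wherever it is allowed.

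**Step 1: stated outpatient minimum by group**

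| Group | C1D22 | C2D1 to C2D15 | C2D22 onward |
|---|---|---|---|
| No listed hypotension | outpatient, none stated | 1 hour | 1 hour |
| Grade 2 at C1D15, no early Grade 3/4, no hypotension needing intervention at C1D22 | inpatient, at least 16 hours | none stated | none stated |
| Grade 3/4 at C1D1, C1D8 or C1D15 | 8 hours if outpatient; inpatient if Grade 2 or greater at C1D15 | 8 hours | none stated |

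The one-hour row starts at Cycle 2, so an outpatient C1D22 dose has no stated minimum even in the first group. Grade 2 hypotension at C1D1 or C1D8 alone does not remove a patient from the one-hour group.

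**Step 2: doses without a stated minimum, over N cycles**

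- Grade 2 at C1D15, from C2D1: 4 doses in each of N − 1 cycles, or 4(N − 1). N = 3 gives 8, N = 4 gives 12, N = 6 gives 20.
- Early Grade 3/4, from C2D22: 1 dose in Cycle 2 and 4 in each later cycle, or 1 + 4(N − 2) = 4N − 7. N = 3 gives 5, N = 4 gives 9, N = 6 gives 17.

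These values of N are illustrations. Counting from C2D1, and taking 3 months as about three 28-day cycles (84 days), the 30-minute provision becomes available around the start of Cycle 5. The counts at N = 4 are therefore the ones it cannot affect.

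**Step 3: 8-hour trigger for a patient with no listed event at C1D1, C1D8 or C1D15**

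| First Grade 3/4 event | Later doses before C2D15 | Section 6.2 item 4 | Table 7-3 alone |
|---|---|---|---|
| C1D22 | C2D1, C2D8 (2 doses) | 8 hours | 1 hour |
| C2D1 | C2D8 (1 dose) | 8 hours | 1 hour |
| C2D8 | none (0 doses) | – | – |

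If C2D15 itself counts, each row gains one dose: 3, 2 and 1. Section 6.2 says *until* C2D15, while Table 7-3 and footnote d say *through* C2D15. The six doses with the anti-hypertensive hold are C1D1, C1D8, C1D15, C1D22, C2D1 and C2D8, so both doses in the first row fall inside it.

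**The case against.** The backstops are substantial.

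- Vital signs after dosing stay mandatory under Section 7.3.4, institutional standards apply, and the investigator may add checks or hospitalize. A reader might infer that the omitted patients go unmonitored. The text does not support that; only the minimum duration and count are missing.
- A reader might infer that every patient with Grade 2 at C1D15 is released without a floor. Section 6.2 item 2 releases only those who had no hypotension needing intervention at the inpatient C1D22 dose. Likewise, early Grade 3/4 patients do have an 8-hour minimum through C2D15. Individual judgement after such supervised doses is a defensible choice.
- A reader might infer that the gap runs on without limit. The 30-minute sentence carries no hypotension qualifier. It names a lowest permitted time after 3 months and presupposes a longer one before. It does not, however, say what that longer time is for the omitted groups.
- A reader might see a contradiction that makes compliance impossible, or think Table 7-3 overrides Section 6.2. Neither holds. Both figures are minimums, so observing for 8 hours satisfies both texts. Section 7.3.4 and footnote d send the reader to Section 6.2. So does Table 6-5 after Grade 3: "Please refer to guidance for continued inpatient monitoring to determine need for continued inpatient monitoring". After Grade 4, "IMCgp100 must be dose reduced or discontinued", with Medical Monitor consultation.
- A first Grade 3/4 event at C1D22 or later may be uncommon. The synopsis places the more severe, dose-limiting toxicity in the first two weeks of dosing. Section 6.9.2 puts cytokine release, including hypotension, generally 2–12 hours after the first three doses. If later events had the same timing, which is an assumption, one hour would miss most of them.

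These points limit the size of the problem but do not remove it. None of the texts says which governs, and Section 6.2 offers no outpatient minimum to fill the gap in Table 7-3. The one-hour figure is the protocol's own standard; the point is only that its scope is wrong.

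**Conclusion.** Both parts hold as defects of wording. Two groups with early hypotension lack a protocol-stated routine minimum that patients without it receive from Cycle 2. Through Cycle 4 this covers 12 doses per patient after Grade 2 at C1D15 with an uneventful inpatient C1D22, and 9 per patient after early Grade 3/4. The 8-hour trigger is stated more narrowly in Table 7-3 and footnote d than in Section 6.2 item 4. For a site relying on Table 7-3 alone, the difference is 1 versus 8 hours at two doses after a first Grade 3/4 event at C1D22, or three if C2D15 counts.

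The counts assume weekly outpatient dosing without delays. The protocol does not give the number of patients in these groups, so no estimate of harm is possible. This is a minor safety correction.

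**What to change.** 1. In Table 7-3, delete the restriction to patients without early hypotension. Make one hour with at least two post-dose measurements the floor for every outpatient dose from C1D22 onward that is not under a stricter rule. Starting at C1D22 also closes the gap at the first possible outpatient dose. Keep the 30-minute provision and the inpatient rule for breaks of more than 2 weeks.
2. In Table 7-3 and Table 7-1 footnote d, make any prior Grade 3 or 4 hypotension event with IMCgp100 dosing the 8-hour trigger, as in Section 6.2 item 4.
3. In Section 6.2 item 4, change *until* to *through* C2D15.

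The cost is edits to one table, one footnote and one list item. In the clinic it adds up to one hour of observation per affected outpatient dose, plus 8 hours at C2D15 where that dose was ambiguous. The trigger change otherwise adds nothing beyond what Section 6.2 already requires.
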